9.2 Setting

The study will take place in China with multiple centers. The study sites will be identified and selected by AbbVie. The study population shall comprise of male and/or female patients who are attending a routine clinical visit and meet all of the inclusion criteria and none of the exclusion criteria. Overall, approximately 52 subjects with clinically diagnosed RA are planned to be enrolled in the study at up to 16 sites.

The recruiting investigators will select potentially eligible patients from consecutive visits within their clinic based on the inclusion and exclusion criteria (Section 9.2.1 and Section 9.2.2). It is the responsibility of each physician to ask every consecutive patient who meets the inclusion criteria of the study to participate to avoid selection bias, and if investigators hold different types of clinics (e.g. routine visit clinics versus emergency clinics), only patients visiting their routine clinics will be used for patient selection. Site personnel should thoroughly assess the eligibility criteria and evidence of this should be stored with the source documentation at site.

Where there is any deviation from the inclusion/exclusion criteria, the patient should be excluded from the study.

9.2.1 Inclusion Criteria:

Patients meeting all of the following inclusion criteria at baseline will be included:

1. Subject has a diagnosis of RA as defined by the 1987 revised ACR classification criteria and/or the ACR/ the European League against Rheumatism (EULAR) 2010 classification criteria (any duration since diagnosis)
2. Male or female subjects \geq 18 years of age who is in compliance with eligibility for adalimumab based on the local label
3. Patients with moderate to severe RA defined as DAS28 (ESR) or DAS28 (CRP) $>$ 3.2
4. Biologically treatment naïve and initiated adalimumab at baseline visit, as per standard daily clinical practice
5. Availability of clinical data of the previous 12 weeks prior to baseline
6. Ability to self-complete patient questionnaires

7. Patients have signed the authorization (or informed consent where applicable) to disclose and use personal health information after been prescribed with adalimumab.

Additional Inclusion Criteria

8. If female subject, is either not of childbearing potential, defined as postmenopausal for at least 1 year or surgically sterile (bilateral tubal ligation, bilateral oophorectomy and/or hysterectomy) or is of childbearing potential and is practicing an approved method of birth control throughout the study and for 150 days after last dose of study drug.
9. Subject is judged to be in good health as determined by the Principal Investigator based upon the results of medical history, laboratory profile, physical examination, chest x-ray (CXR), and a 12-lead electrocardiogram (ECG) performed during Screening;
10. Subject has a negative TB Screening Assessment. If the subject has evidence of a latent TB infection; the subject must initiate and complete a minimum of 4 weeks of an ongoing TB prophylaxis or have documented completion of a full course of TB prophylaxis, prior to Baseline

9.2.2 Exclusion Criteria:

Patients meeting any of the following exclusion criteria at baseline will be excluded:

1. Patients who are pregnant or breast feeding at enrolment or wish to become pregnant in the next 24 weeks
2. Participation in any RA-related clinical trial at the time of enrolment, at baseline or at any point during the past 24 weeks prior to baseline
3. Patients, who in the clinician's view, may not be able to accurately report their QoL or prior resource utilization
4. Patients, who in the clinician's view, may not be able to adhere to adalimumab therapy over 24 weeks

Additional Exclusion Criteria

5. Subject has been treated with any investigational drug of chemical or biologic nature within a minimum of 30 days or five half-lives (whichever is longer) of the drug prior to the Baseline Visit
6. Prior exposure to biologics that have a potential or known association with PML (i.e., natalizumab (Tysabri®), or rituximab (Rituxan)
7. Positive pregnancy test at Baseline
8. Patients with contraindication or are not appropriate to use adalimumab according to local label or investigators' judgment

9.2.3 Investigator Selection Criteria

Selection of investigators will be made based on qualification by training and experience. AbbVie will provide a list of clinicians that would be able to assist in recruiting in a timely manner. AbbVie will contact each clinician to obtain their participation in the study and provide an expected number of patients to be enrolled from that clinic. The ethical review boards recognized by the respective participating sites are required to review and approve the study and patient informed consent.

9.2.4 Study Procedures

The study procedures outlined in Table 1 will be discussed in detail in this section with the exception of adverse events procedures (discussed in Section **Error! Reference source not found.**).

[figure not shown]
9.2.4.1 Informed Consent

Prior to any study-related data being collected, patient authorization (or informed consent where applicable) will be reviewed, signed and dated by the patient and the person who administered the patient authorization (or informed consent). A copy of the signed patient authorization (or informed consent) will be given to the patient and the original will be placed in the patient's medical record.

9.2.4.2 Patient Assignment

Once the recruiting clinician has obtained the subject's authorization to release medical information and written consent to participate in the study, the clinician will be asked to complete an inclusion and exclusion form (**Error! Reference source not found.**) for patients, thus confirming the patient's eligibility to participate in this study. Each participating patient will be assigned a 3-digit patient identification number. The numbers should be assigned in sequential, ascending order per site as shown below:

- Site ID; and
- Patient ID: First eligible patient number will be 001, and then the second patient number would be 002

Site ID Patient ID

9.2.4.3 Investigator Recruitment

AbbVie will provide a list of clinicians that would be able to assist in recruiting in a timely manner. AbbVie will contact each clinician to obtain their participation in the study and provide an expected number of patients to be enrolled from that clinic. The ethical review boards recognized by the respective participating sites are required to review and approve the study and patient informed consent.

9.2.4.4 Study site monitoring

AbbVie will closely track enrolment progress for monthly reporting. AbbVie will work closely with the study coordinator at each site to ensure they check the forms when returned from the patients and physicians (e.g., all questions were answered). AbbVie will also be available to answer questions and follow up with the sites if the recruitment process is slow or if there are any errors on the forms. Periodic phone follow-up will be conducted to ensure data collection completeness and quality.

9.2.4.5 Patient Selection

The recruiting investigators will select potentially eligible patients from consecutive visits within their clinic based on the inclusion and exclusion criteria (Section 9.2.1 and Section 9.2.2). It is the responsibility of each physician to ask every consecutive patient who meets the inclusion criteria of the study to participate to avoid selection bias, and if investigators hold different types of clinics (e.g. routine visit clinics versus emergency clinics), only patients visiting their routine clinics will be used for patient selection. The intent is to enroll patients who have been prescribed adalimumab upon the physicians' own discretion.

Medical and Surgical History

A detailed medical history with respect to TB exposure needs to be documented. This information needs to include BCG vaccination, cohabitation with individuals who have had TB, and/or who reside or work in TB endemic locations.

Pregnancy Tests

At the Baseline Visit, subjects of childbearing potential will have a urine pregnancy test performed locally by designated study personnel. If any urine pregnancy test is positive, a

serum pregnancy test will be performed. A lactating or pregnant female will not be eligible for participation or continuation in this study.

All women of childbearing potential will have a repeat urine pregnancy test at the final Study Visit performed locally by designated study personnel.

9.2.4.6 Data Collection

AbbVie will coordinate data collection with each site. At study initiation (Baseline, D0), patients will be asked to provide their written informed consent.

When available, the PRO data as observed will be collected -. The CRF completed by physicians will be returned to the study coordinator/nurse at each site as well.

All data filled in by the patient and physician will be collected by the study coordinator/nurse at each site and returned directly to AbbVie.

All patient and clinician data will be handled preserving confidentiality.

9.2.4.7 Study Documents

Clinical case report form (CRF)

The clinical CRF will document the patient's current status (moderate, severe RA), Disease Activity Score in 28 joints (DAS28), prior and current treatments and other relevant clinical and demographic data to be used in segmenting the population during analysis.

To calculate the DAS28 the physician or specialist nurse will:

1. Count the number of swollen joints (out of the 28)
2. Count the number of tender joints (out of the 28)
3. Take blood to measure the erythrocyte sedimentation rate (ESR) or C reactive protein (CRP); the latest measurement in the medical records may also be used if a blood draw is not standard for that visit
4. Ask the patient to make a 'global assessment of health' which will be indicated by marking a 10 cm line between very good and very bad

The physician or specialist nurse will then mark each component score on the CRF and the DAS28 score if calculated (an online scoring calculator for the DAS28 can be found at <http://www.das-score.nl/das28/DAScalculators/dasculators.html>).

The DAS28 will be scored using the following formula:

$$\text{DAS28(CRP)} = 0.56 * \text{sqrt}(\text{tender28}) + 0.28 * \text{sqrt}(\text{swollen28}) + 0.36 * \ln(\text{CRP}+1) + 0.014 * (\text{Patient Global assessment of Health in mm})+0.96$$

$$\text{DAS28(ESR)} = 0.56 * \text{sqrt}(\text{tender28}) + 0.28 * \text{sqrt}(\text{swollen28}) + 0.70 * \ln(\text{ESR}) + 0.014 * (\text{Patient Global assessment of Health in -mm})$$

DAS28 scores will be interpreted using the following categorization:

- Remission: $\text{DAS28} \leq 2.6$
- Low Disease activity: $2.6 < \text{DAS28} \leq 3.2$
- Moderate Disease Activity: $3.2 < \text{DAS28} \leq 5.1$
- High Disease Activity: $\text{DAS28} > 5.1$

The full CRF is presented in **Error! Reference source not found.**

PRO questionnaires

The following PRO questionnaires will be included in the patient questionnaire packet.

Health Assessment Questionnaire Disability Index (HAQ DI)

The HAQ DI is a patient-reported questionnaire to assess functioning impacted by RA. It includes the categories of dressing and grooming, arising, eating, walking, hygiene, reach, grip and common daily activities. It asks patients about the amount of difficulty they experience in these activities as well as the use of aids and/or devices. The HAQ also has a numeric rating scale (NRS) (13) to assess pain on a scale from 0 to 10. Self-administered by the patient, the completion time is approximately 3-4 minutes. The full version of HAQ DI is presented in **Error! Reference source not found.**

Short Form (36) Health Survey (SF-36)

The SF-36 is a patient-reported questionnaire of patient health-related QoL. It measures generic health concepts relevant across age, disease, and treatment groups. There are 36 items in total and the recall period is the last 4 weeks. The SF-36 consists of eight scaled scores, which are the weighted sums of the questions in their section. Each scale is directly transformed into a 0-100 scale. Completion time for the SF-36 is approximately

10 minutes. The full version of SF-36 is presented in **Error! Reference source not found.**

EuroQol 5 dimension, 3 level quality of life questionnaire (EQ-5D-3L)

The EQ-5D-3L measures the patient's overall health state in a descriptive system of health-related QoL states consisting of five dimensions (mobility, self-care, usual activities, pain/discomfort, and anxiety/depression) each of which can take one of three responses. The responses record three levels of severity ('no problems', 'some problems', and 'extreme problems') within a particular EQ-5D-3L dimension (14, 15). In addition, a VAS rates current health state between 0-100. The EQ-5D-3L results can be converted to health utility scores. Completion time for the EQ-5D-3L is approximately 2-3 minutes. The full version of EQ-5D-3L is presented in **Error! Reference source not found.**

Work Productivity and Activity Impairment (WPAI)

The WPAI is a patient-reported questionnaire to measure work and activity impairment during the past seven days. It determines employment status, hours missed from work due to the disease (i.e. RA), hours missed from work for other reasons, hours actually worked, the degree to which the disease affected work productivity while at work and the degree to which the disease affected activities outside of work. Additional questions around employment status will be incorporated into the survey. The completion time for the WPAI is approximately 2-5 minutes. The full version of WPAI is presented in **Error! Reference source not found.**

All of the above questionnaires will be used with the validated Chinese version.

Patient Global Impression of Change (PGIC)

The PGIC measures the patient's perceptions of changes in their disease. It consists of one question asking about the change in their condition; for this study, the base will be "since you initiated your adalimumab treatment". The completion time for the PGIC is less than 1 minute. The full version of PGIC is presented in **Error! Reference source not found.**

Patient Treatment Satisfaction Questions

The patient treatment satisfaction questions were developed de novo for this study and are not considered "validated" questions. Self-administered by the patient, the completion time for the patient treatment satisfaction questions is approximately 1-2 minutes. The full version of patient treatment satisfaction questions are presented in **Error! Reference source not found.**

Healthcare Resource Utilization (HCRU) Questionnaire

The HCRU questionnaire will collect data on the healthcare resources consumed in the prior 3 months, as recall beyond 3 months may be problematic in an older population (16). HCRU collection will include data such as the number of physician visits and to which physician (GP, specialist), Emergency Department visits, hospitalizations, and other drugs as well as devices and aids purchased to assist in their mobility due to RA. The HCRU questionnaire will be part of the patient questionnaire and will be distributed to patients together with the PRO questionnaires (Appendix D to Appendix I). The full HCRU questionnaire is presented in **Error! Reference source not found.J** and will be used with the validated Chinese version.

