9.1.1 Study Activities

Table 1 Study Activities (Day 1/Baseline Through 6 months)

	Data Collection/Observation	Baseline ^a	Week 12 (V2) ± 7 days	Week 24 (V3) ± 7 days	Early Termination / Drop out	70 days after the Week 24 or the last dose	150 days after the Week 24 or the last dose
Clinician Packet	Inclusion/exclusion form	X					
	Clinical history/patient demographics	X					
	Comorbidities	X					
	DAS28 (ESR) or DAS28 (CRP)	X	X	X	X		
Patient Packet	EuroQoL 5-Dimension (EQ-5D)	X	X	X	X		
	Short Form 36-Item Health Survey (SF-36)	X	X	X	X		
	Health Assessment Questionnaire (HAQ)	X	X	X	X		
	Work Productivity and Activity Impairment Questionnaire (WPAI)	X	X	X	X		
	Healthcare Resource Utilization (HCRU)	X	X	X	X		
	Patient Global Impression of Change (PGIC)		X	X	X		
	Patient Treatment Satisfaction Questions	X	X	X	X		
Clinical n	Adverse events (including malignancy)	←				→	
	Pregnancy	←					→

a. The Baseline visit date will serve as the reference for all subsequent visits. A \pm 7 day window is permitted around scheduled study visits.

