9.7.6 Additional Secondary Endpoint Analysis

Additional efficacy analysis include:

- Change in HAQ DI score at 24 weeks after the initiation of adalimumab, in those patients continuing on adalimumab, compared with those patients not continuing on adalimumab. The mean changes in these two groups will be compared using an independent t-test.
- Healthcare resource utilization will be described using number and percentage within each category (number of consultations, number of procedures received, number of surgeries, number of hospitalizations and length of stay, number of concomitant medications)
- Associations between disease severity and PROs
- Associations between change in disease severity and change in PROs

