### **3.5.2 Exposure/Independent Variables of Interest**

- **Patient demographics (if data available)**
  - Date of birth
  - Age at baseline
  - Age groups
  - Gender at birth
  - Marital status (married, unmarried)
  - Medical plan type
    - ✓ The type of healthcare plan each patient is enrolled in at baseline will be determined, including National/Public insurance, Private insurance, Employer benefits, and Other
- **Clinical characteristics**
  - Initial Diagnosis of Rheumatoid Arthritis (RA)
    - ✓ Year of initial diagnose
  - Initiation of Adalimumab
    - ✓ First time administration (DD/MM/YYYY)
    - ✓ Dosage of first injection (in mg)
  - Disease status of RA
    - ✓ Moderate (defined as Disease Activity Score in 28 Joints (DAS28) between 3.2 and 5.1)
    - ✓ Severe (DAS28>5.1)
  - Erythrocyte sedimentation rate (ESR) (in mm/hour)
  - C reactive protein (CRP) (in mg/L)
  - Disease Activity Score in 28 joints (DAS28)

To calculate the DAS28, the physician or specialist nurse will:

1. Count the number of swollen joints (out of the 28)

2. Count the number of tender joints (out of the 28)
3. Take blood to measure the erythrocyte sedimentation rate (ESR) or C reactive protein (CRP); the latest measurement in the medical records may also be used if a blood draw is not standard for that visit
4. Ask the patient to make a 'global assessment of health' which will be indicated by marking a 10 cm line between very good and very bad

The physician or specialist nurse will then mark each component score on the CRF and the DAS28 score if calculated (an online scoring calculator for the DAS28 can be found at <http://www.das-score.nl/das28/DAScalculators/dasculators.html>).

The DAS28 will be scored using the following formula:

$$\text{DAS28} = 0.56 * \text{sqrt}(\text{tender28}) + 0.28 * \text{sqrt}(\text{swollen28}) + 0.70 * \ln(\text{ESR or CRP}) + 0.014 * (\text{Global assessment of Health})$$

DAS28 scores will be interpreted using the following categorization:

- ✓ Remission:  $\text{DAS28} \leq 2.6$
  - ✓ Low Disease Activity:  $2.6 < \text{DAS28} \leq 3.2$
  - ✓ Moderate Disease Activity:  $3.2 < \text{DAS28} \leq 5.1$
  - ✓ High Disease Activity:  $\text{DAS28} > 5.1$
- comorbidities
- ✓ Myocardial infarction
  - ✓ Congestive heart failure
  - ✓ Peripheral vascular disease
  - ✓ Cerebrovascular disease
  - ✓ Dementia
  - ✓ Chronic pulmonary disease
  - ✓ Connective tissue disease
  - ✓ Ulcer disease
  - ✓ Mild liver disease
  - ✓ Diabetes

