- Additionally, in Excel Table 10.2, separate bivariate linear regression models will be estimated to identify the association between change in DAS28 and change in each of the PROs at 12 and 24 weeks after baseline respectively. If normality assumption for the residual of regression is violated, Spearman correlation coefficients and p-values will be estimated instead.
- In Excel Table 11, separate multivariate generalized linear models (GLM) will be estimated to test for the differential changes in primary and secondary efficacy outcomes after baseline, across the subgroups defined by the potential modifiers, including age, gender, baseline severity, and other diagnoses/comorbidities.

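### DAS28 may be scored with ESR at one visit and CRP at another, and the SAP analyses its change with no same-marker condition, so a marker switch alone can create a false change in either direction

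*Protocol*

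**What the plan says.** Protocol 9.2.4.7 describes the DAS28 assessment. Its third step is to "Take blood to measure the erythrocyte sedimentation rate (ESR) or C reactive protein (CRP"), and it adds that "the latest measurement in the medical records may also be used if a blood draw is not standard for that visit". Table 1 in Protocol 9.1.1 has a single row, "DAS28 (ESR) or DAS28 (CRP"), marked for baseline, Week 12, Week 24 and early termination. Eligibility (9.2.1) also accepts either version above 3.2.

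Protocol 9.2.4.7 gives a separate equation for each version but only one set of category cut-offs (2.6, 3.2, 5.1). It also has staff enter the component scores on the CRF, along with the DAS28 itself where it has been calculated.

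Change in disease severity to Week 24 is an additional secondary variable (Protocol 9.3), and 9.7.6 plans "Associations between change in disease severity and change in PROs". SAP 5.5 measures severity by DAS28 and, for Table 10.2, models the "association between change in DAS28 and change in each of the PROs at 12 and 24 weeks after baseline". SAP 3.5.2 lists ESR and CRP as separate variables but defines one DAS28 equation into which either is entered.

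Neither document requires the same marker within a patient, names a preferred version, says what to do when versions differ, or separates results by version.

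**The concern.** A change score is meaningful only if both visits are measured on the same scale. Here the scale may differ between visits, because the two protocol equations treat their marker differently: one uses 0.70×ln(ESR) with no constant, the other 0.36×ln(CRP+1) plus 0.96. A patient whose disease has not moved can therefore have a non-zero DAS28 change simply because a different test was on file.

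At stake are the change-in-severity variable and the Table 10.2 associations. There is a second, between-patient route. If some patients have an ESR-based baseline and others a CRP-based one, equal disease can yield different baseline DAS28. That value serves as the covariate in the sensitivity ANCOVA, defines the moderate/severe subgroup (Protocol 9.7.3), and enters SAP Tables 10.1 and 11.

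This is distinct from the SAP's use of a single equation and from the use of older laboratory values. It would remain if both protocol equations were applied correctly to current samples.

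**Working it through.** The documents give no figure for DAS28 change or for ESR/CRP agreement, so there is no stated result to reproduce. The check uses the documents' own equations.

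**Inputs.** The marker terms come from Protocol 9.2.4.7. ESR is in mm/hour and CRP in mg/L, the units in SAP 3.5.2 ("C reactive protein (CRP) (in mg/L")); the protocol's CRP equation states no unit. The ESR/CRP pairs are assumptions, chosen to show both signs.

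**Gap under the protocol equations.** Joint counts and the patient global score have the same coefficients in both versions and cancel, leaving

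gap = DAS28(ESR) − DAS28(CRP) = 0.70×ln(ESR) − 0.36×ln(CRP+1) − 0.96

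| ESR / CRP (assumed) | 0.70×ln(ESR) | 0.36×ln(CRP+1) + 0.96 | Gap |
|---|---|---|---|
| 10 / 3 | 1.612 | 1.459 | +0.15 |
| 20 / 5 | 2.097 | 1.605 | +0.49 |
| 40 / 10 | 2.582 | 1.823 | +0.76 |
| 60 / 10 | 2.866 | 1.823 | +1.04 |
| 10 / 10 | 1.612 | 1.823 | −0.21 |
| 10 / 40 | 1.612 | 2.297 | −0.69 |

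Over a wider assumed grid (ESR 10 to 80, CRP 1 to 40) the gap runs from −0.69 to +1.86. It is zero only along one curve: CRP about 5.1 at ESR 10, 22.5 at ESR 20 and 89.6 at ESR 40.

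**Effect of a switch in an unchanged patient.** Moving from ESR to CRP gives an apparent change of minus the gap; the reverse switch gives plus the gap. With the same marker at both visits the change is exactly 0.

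**Worked example (assumed values).** Take 8 tender joints, 6 swollen joints, global 60 mm, ESR 40 and CRP 10 at both visits. The shared part is 0.56×√8 + 0.28×√6 + 0.014×60 = 1.584 + 0.686 + 0.840 = 3.110.
- DAS28(ESR) = 3.110 + 2.582 = 5.69, high activity.
- DAS28(CRP) = 3.110 + 1.823 = 4.93, moderate activity.
- An ESR-to-CRP switch therefore shows −0.76 with no change in disease. If these were the baselines of two patients with equal disease, they would fall on opposite sides of 5.1.

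**Under the SAP equation as written.** Both markers take the term 0.70×ln(·), so the gap is 0.70×ln(ESR/CRP): +0.84 at 10/3, +0.97 at 40/10, +1.25 at 60/10, 0.00 at 10/10 and −0.97 at 10/40. Using one equation does not remove the problem.

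**Effect on a mean.** If a share p of patients switches in one direction with gap g, the mean change is biased by p×g in absolute size. With g = 0.76 this is 0.08, 0.19 and 0.38 at p = 10%, 25% and 50%. These values of p are illustrations only.

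**The case against.** The best case on the other side has five parts.

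- **The marker should usually be visible already.** The components are entered on the CRF and the SAP holds ESR and CRP as separate variables. This stands, and it makes the repair cheap. It does not close the gap, because no rule says which value enters the change score when the markers differ or when both are present. The CRF is a separate document that cannot be checked here.
- **The direction is not fixed.** A reader might infer that moving from ESR to CRP usually produces a false improvement. The documents give no joint distribution of ESR and CRP, and pairs such as 10/10 and 10/40 give the opposite sign. Only a false change in either direction is supported.
- **The reach is limited.** A reader might infer that the main result is at risk, or that false shifts between activity categories will be reported. The primary paired HAQ DI test uses no DAS28. The SAP tabulates DAS28 categories at baseline only and lists no DAS28 response or category-shift table. In Table 10.2, switching unrelated to PRO change would mainly add noise and weaken the association. All of this stands.
- **The frequency is unknown.** No text shows that switching is expected. Routine-practice visits at up to 16 sites, with values taken from records, make it possible and no more than that.
- **A compulsory marker would conflict with the design.** Protocol 9.1 asks sites for nothing beyond current practice, and 12.5 says the study involves no direct intervention in laboratory testing. This also stands, and it limits what the protocol can ask of sites.

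**Conclusion.** The point holds as a measurement weakness in secondary and exploratory analyses. Followed as written, the plan can record a non-zero DAS28 change in a patient whose disease has not changed. For the tabulated pairs the discrepancy runs from −0.69 to +1.04 under the protocol's equations. That is not small beside a moderate-activity band 1.9 wide (3.2 to 5.1).

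Directly affected are the protocol's change-in-severity variable and SAP Table 10.2. Through mixed versions at baseline, the sensitivity ANCOVA, the moderate/severe subgroup and Tables 10.1 and 11 can be affected. The SAP's document history says the ANCOVA uses DAS28 as a continuous variable, so there the exposure is to the shift in score and not to the 5.1 cut-off.

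The size rests on assumed ESR/CRP pairs and on CRP in mg/L. The existence of the gap rests only on the printed equations. The documents do not support any statement about how many patients would switch, the net direction of bias, or harm to the primary result or the sample size.

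**What to change.** **SAP 3.5.2.** Identify the DAS28 version at each visit from the recorded ESR or CRP, and compute each version with its own protocol equation. This requires the SAP's single equation to be reconciled with the protocol's two.

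**SAP 5.5.** Compute change in DAS28 only from same-version pairs, using whichever version is available at both visits. Set it to missing otherwise. If both versions are available at both visits, state in advance which one is analysed. Report the number of patients by version at each visit and the number without a same-version pair. Present the results that use baseline severity (sensitivity ANCOVA, moderate/severe subgroup, Tables 10.1 and 11) by version. With about 52 patients the by-version results will be descriptive.

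**Protocol 9.2.4.7 and Table 1.** Ask sites only to record which marker was used, and to report the baseline marker again where routine practice provides it. Do not require an additional test.

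**Cost.** A few lines of SAP text and, if the CRF does not already show it, one field for the marker. Patients without a same-version pair drop out of the DAS28-change analysis only; the HAQ DI change analysis keeps them. The planned sample size does not depend on DAS28 and is unchanged.
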